1. LIST OF ABBREVIATIONS AND DEFINITION OF TERMS

The following abbreviations and special terms are used in this study protocol.

Abbreviation	Explanation
ADA	Anti-drug antibody
ADAMTS13	a disintegrin and metalloproteinase with a thrombospondin type 1 motif, member 13
AE	Adverse event
APt	Activated partial thromboplastin time
ATGAM	Equine anti-thymocyte globulin
AUC _t	Area under serum concentration time curve from t=0 to last timepoint
BMI	Body mass index
BW	Body weight
CKD	Chronic kidney disease
C _{max}	Maximum serum concentration
CRF	Case report form (electronic/paper)
CRO	Contract research organisation
CRP	C-reactive protein
CSR	Clinical study report
CTCAE	Common toxicity criteria for adverse events
CV	Coefficient of variation
DLT	Dose Limiting Toxicity
█	█
ECG	Electrocardiogram
EOS	End of study
FAS	Full analysis set
FRET	Fluorescence resonance energy transfer
GCP	Good clinical practice
HIV	Human immunodeficiency virus
HLA	Human leukocyte antigen
HR	Heart rate
ICF	Informed consent form
ICH	International conference on harmonisation
IdeS	Immunoglobulin G-degrading enzyme of Streptococcus pyogenes
IMC	Internal Monitoring Committee
IMP	Investigational medicinal products

Abbreviation	Explanation
IUD	intrauterine device
IUS	intrauterine system
IVIg	Intravenous immunoglobulin
█	█
MAHA	microangiopathic haemolytic anemia
MedDRA	Medical dictionary for regulatory activities
MSD	Meso Scale Diagnostic
NOAEL	No observed adverse effect level
PBS	Phosphate buffered saline
PD	Pharmacodynamics
PE	Plasma Exchange
PK	Pharmacokinetics
PK (INR)	Prothrombine complex (internationally normalised ratio)
PPS	Per protocol set
PRA	Panel reactive antibody
rATG	Rabbit anti-thymocyte globulin
SAE	Serious adverse event
SAP	Statistical analysis plan
SAR	Serious adverse reaction
SOC	System organ class
SUSAR	Suspected unexpected serious adverse events
TEAE	Treatment emergent adverse event
TTP	Thrombotic thrombocytopenic purpura
vW	von Willebrand factor

3. INTRODUCTION

3.1 Disease and Patient population

Thrombotic thrombocytopenic purpura (TTP) is a rare life-threatening thrombotic disorder of the blood-coagulation system, causing extensive microscopic clots to form in the small blood vessels throughout the body. These small blood clots, called thrombi, can damage many organs including the kidneys, heart and brain. TTP is a medical emergency that is almost always fatal if appropriate treatment is not initiated promptly. Treatment with plasma exchange (PE) and glucocorticoids reduces the mortality to between 10% and 15% (George 2012).

In the majority of patients, TTP is a result of autoantibody-mediated inhibition of a disintegrin and metalloproteinase with a thrombospondin type 1 motif, member 13 (ADAMTS13). This type of TTP is called acquired TTP. In a minority of patients, TTP is due to deleterious mutations in ADAMTS13; i.e., hereditary or congenital TTP.

Acquired TTP is characterized by thrombocytopenia and microangiopathic haemolytic anemia (MAHA) without an obvious cause, and may include fever, mild renal failure, and neurologic deficits (Sayani and Abrams 2015). The majority of the patients suffering from acquired TTP develop autoantibodies that bind and neutralize the proteolytic activity of ADAMTS13 and/or accelerate its clearance *in vivo* (Scheiflinger, Knöbl et al. 2003). Recently published data suggest that depletion of ADAMTS13 antigen, rather than enzyme inhibition, is the dominant pathogenic mechanism in acquired TTP (Thomas, de Groot et al. 2015). A severe deficiency of plasma ADAMTS13 activity (less than 5%) and the presence of autoantibodies are considered to be highly specific for the diagnosis of acquired TTP (Hovinga and Lämmle 2012). Anti-ADAMTS13 antibodies are present in the majority of patients (94–97%) suffering from acquired TTP and are considered to be strongly involved in the pathogenesis of the disease (Verbij, Fijnheer et al. 2014).

Early intervention improves prognosis dramatically. As a result, measurement of serum ADAMTS13 activity is not performed for diagnosis, as turn-around time tends to be long and awaiting results may delay life-saving treatment. However, measurement of ADAMTS13 and antibodies to ADAMTS13 are conducted for diagnostic confirmation.

3.2 Current Treatments

Due to the rarity of the disease very few randomized studies with definitive conclusions have been performed in TTP and its management is largely based on clinical experience (Verbij, Fijnheer et al. 2014). The mainstay of treatment is PE, while monitoring [REDACTED] and [REDACTED]. The ADAMTS13 assays may not be immediately available. Therefore, the treatment must be based on clinical symptoms and other laboratory tests and the decision to start PE should not wait for results of the ADAMTS13 assay (Sayani and Abrams 2015). In addition to plasma exchange, other methods are necessary to treat patients because of high frequency of relapse, especially in patients with high titre inhibitory antibodies. Most patients are treated with steroids and rituximab is part of standard therapy (Said, Haddad et al. 2014). Treatment must be started as soon as possible after diagnosis or even suspicion of TTP. [REDACTED], [REDACTED] level and ADAMTS13 results are indicators of disease severity and forms the basis for treatment decision. Immunosuppressive therapies like corticosteroids, anti-CD20 or cyclosporine are also being used in the treatment of acquired TTP.

3.2.1 Plasma Exchange

The mortality rate of TTP prior to the use of PE was approximately 90 percent but is now down to 15 percent or less (Sayani and Abrams 2015). PE is the standard treatment in acquired TTP and is considered to remove circulating antibodies to ADAMTS13 and the subsequent plasma replacement, replenish the deficient ADAMTS13 (Verbij, Fijnheer et al. 2014). Despite the rarity of TTP, these patients are the single largest consumers of plasma, with an average volume per episode of 40 L (Scully 2014). PE is performed once or twice daily until the [REDACTED] has recovered. Complications associated with plasma exchange (incidence 10%) are mostly related to the use of central venous catheter and the plasma replenishment (Said, Haddad et al. 2014).

According to the 2012 American Society of Apheresis Consensus Conference on TTP, response is defined as a [REDACTED] of at least 150 000/mL for 2 consecutive days, a normal or near normal [REDACTED], and stable or improving neurologic symptoms. The number of treatments needed varies, and may be higher in patients with high antibody titre (Sayani and Abrams 2015).

3.2.2 Steroids

Glucocorticoids are used in the acute management of acquired TTP and should be started directly together with PE (Sayani and Abrams 2015). Steroids are used to target the autoimmune component of the disease and are believed to suppress the production of anti-ADAMTS13. The effect of steroids may also be due to down-regulation of various cytokines involved in TTP pathogenesis (Verbij, Fijnheer et al. 2014).

3.2.3 Rituximab

Anti-CD20 (rituximab) was initially used in patients with a suboptimal response to standard treatment, such as those with refractory or relapsed disease (Verbij, Fijnheer et al. 2014) but is now standard of care as up-front treatment. Anti-CD20 therapy has been demonstrated to be effective in prolonging the duration of remission as well as decreasing the frequency of remission (Scully, McDonald et al. 2011).

3.3 IdeS

Immunoglobulin G-degrading enzyme of *Streptococcus pyogenes* (IdeS) is an IgG specific endopeptidase. Cleavage of IgG generates one F(ab')₂- and one homodimeric Fc-fragment and efficiently neutralizes Fc-mediated activities of IgG (HMed doc. No. 2012-003) (von Pawel-Rammingen, Johansson et al. 2002, Wenig, Chatwell et al. 2004, Vincents, von Pawel-Rammingen et al. 2004). IdeS-mediated IgG degradation constitutes a novel therapeutic principle for the treatment of IgG-driven human diseases.

Hansa Medical AB has performed *in vitro* studies and clearly demonstrated that IdeS effectively cleaves purified IgG as well as IgG in serum from human and rabbit. IdeS is very specific in that no other substrate has been found (HMed Doc. No. 2012-003).

3.4 IdeS Clinical Studies

A phase I study first in man single ascending dose study in 29 healthy subjects showed that IdeS was safe and well tolerated in doses up to 0.24 mg/kg body weight (BW). The study demonstrated that IdeS could be administered at 0.24 mg/kg BW with a favourable safety profile. It also showed that IdeS could effectively reduce the levels of plasma IgG and that newly synthesised IgG was not detectable until two weeks after dosing. At the two highest

doses, 0.12 and 0.24 mg/kg BW, IdeS completely cleaved the pool of plasma IgG within 14 minutes after initiation of infusion and the level of intact IgG was reduced to less than 5% of its original level. In addition, newly synthesized IgG was not detectable until two weeks after dosing (HMed Doc. No. 2014-003). The data clearly indicates that a single dose of IdeS is superior to both plasmapheresis and immunoadsorption with respect to efficiency and rate of plasma IgG reduction. Since IdeS degrades IgG there was concern that study subjects would have an increased risk of infection and that subclinical infections (e.g., pneumococci) would pose a problem. Therefore, subjects received antibiotic prophylaxis until plasma IgG levels had returned to levels ≥ 4.5 g/L and there were no signs of an increased rate of infections within the study group. The adverse events that were reported, none of which were reported as serious, were as anticipated from the biological nature of the drug. Hence, headache and fatigue were more common in the IdeS treated subjects compared to placebo. One possible infusion reaction was reported among the placebo treated subjects and one among the IdeS treated, the latter resolved within 60 minutes after treatment with antihistamine and glucocorticoids and the infusion was completed. All adverse events were mild or moderate.

One phase II study was completed at Uppsala University Hospital, Sweden in March 2015. The study was a single arm study with ascending doses of IdeS in 8 chronic kidney disease (CKD) patients on the kidney transplantation waiting list and sensitized to human leucocyte antigens (HLAs). The patients enrolled were diagnosed with CKD, in dialysis and on the waiting list for a kidney transplant. However, transplantation was not part of the study protocol. The study showed that one or two doses of IdeS at 0.25 mg/kg BW in the majority of the patients resulted in HLA antibody levels, acceptable for transplantation within 24 hours from dosing. In addition, in all patients having a significant pre-dose panel-reactivity the percentage panel reactive antibody (PRA) was reduced one hour after IdeS treatment. It was also concluded that in the majority of patients the complement dependent cytotoxic crossmatches were converted to negative already one hour after a single dose of IdeS (0.12 or 0.25 mg/kg BW) and the crossmatches remained negative for one week. There were a total of five SAEs reported in the study of which four were classified as probable or possible related to study drug, i.e., suspected serious adverse reactions (SARs). Three of the SARs were infections and one myalgia. Two phase II studies using IdeS in sensitized patients prior to kidney transplantation are currently ongoing in Uppsala, Sweden and Los Angeles, US.

3.5 Overdose

An overdose is a dose in excess of the dose specified in the protocol. There are no data on overdosing of IdeS. There is no known antidote but depletion of IgG can be restored with intravenous immunoglobulin (IVIg). In the event of an overdose the patient should be monitored closely and treated symptomatically. This should be recorded as follows:

- An overdose with associated adverse events (AEs) is recorded as the AE diagnosis/symptoms on the relevant AE modules in the case report form (CRF)
- An overdose without associated symptoms is only reported in the patient file

3.6 Study Rationale and Discussion on Overall Study Design

Asymptomatic patients with low ADAMTS13 activity are at significant risk of relapse. Patients may never have recovered a normal ADAMTS13 activity after the acute episode, or more commonly, ADAMTS13 activity may fall in remission, predisposing to clinical relapse. Elective rituximab is used in this situation to clear anti-ADAMTS13 antibodies and normalise ADAMTS13 activity, thus reducing the risk of a clinical relapse. It is possible that addition of IdeS will be an advantage in asymptomatic patients by quickly removing ADAMTS13 antibodies from circulation, thus allowing ADAMTS13 to return to normal levels.

The primary objective of the proposed pilot study is to monitor safety and tolerability in patients diagnosed with asymptomatic antibody-mediated TTP with low ADAMTS13 activity after receiving single intravenous doses of IdeS. The secondary objective is to investigate IdeS efficacy in significantly increasing ADAMTS13 activity and decreasing ADAMTS13 antibody levels in patients with asymptomatic antibody-mediated TTP. In the current study this will be investigated in asymptomatic patients with reduced levels of ADAMTS13 activity and measurable levels of circulating ADAMTS13 antibodies.

Eligible patients must have ADAMTS13 activity levels less than 10% of normal levels. Each patient will receive one dose of 0.25 mg/kg BW IdeS. Following an evaluation of safety and efficacy in 3 patients dosed at 0.25 mg/kg, there will be a possibility to increase the dose to 0.5 mg/kg for the next 3 patients. The dose will be given as a single intravenous infusion (for details see section 7, Study conduct). Single doses up to 0.24 mg/kg BW (maximum dose tested) has previously been given to healthy volunteers and doses up to two times 0.25 mg/kg BW has been given to CKD patients. In asymptomatic patients with acquired TTP it is expected that the pharmacokinetic of IdeS pharmacokinetics is similar to healthy subjects.

Based on the current knowledge, including experience from completed and ongoing clinical studies, it is expected that IdeS will degrade IgG into F(ab')₂ and Fc fragments across all compartments allowing a rapid and potent reduction of the specific anti-ADAMTS13 antibodies. The F(ab')₂-fragment created by IdeS treatment will not be able to clear ADAMTS13 via Fc-mediated activities. However, the remaining F(ab')₂ seen in serum after 24-48 hours may still have the capacity to block ADAMTS13 activity for example by interfering with binding to von Willebrand (vW) factor. However, as shown by Thomas et al. (Thomas, de Groot et al. 2015) depletion of ADAMTS13 antigen, rather than enzyme inhibition, is the dominant pathogenic mechanism in acquired TTP.

The hypothesis is that the reduction in anti-ADAMTS13 IgG will translate into a rise in ADAMTS13 activity and hence reduce the risk of clinical relapse.

3.7 Risk/Benefit and Ethical Assessment

A starting dose of 0.25 mg/kg BW has been selected for this study. The phase I study did not identify any dose limiting factors even at the highest tested dose (0.24 mg/kg BW) and CKD patients in a completed phase II study in Sweden were exposed to a total dose of 0.5 mg/kg BW with acceptable safety profile. In addition, the doses of 0.25 mg/kg and 0.5 mg/kg BW are well covered by the no observed adverse effect level (NOAEL) of 2.0 mg/kg BW obtained in toxicology studies. The pharmacokinetics (PK) of IdeS in asymptomatic TTP patients is expected to be similar to what is observed in healthy subjects, thus, a starting dose of 0.25 mg/kg BW is considered to be safe.

Since IdeS effectively removes the IgG pool, there may be an increased risk of infection. In order to minimise the risk for bacterial infections all patients treated with IdeS will receive a two-week regimen of prophylactic antibiotics following IdeS dosing. Patients will be screened for viruses (Hepatitis B, C and human immunodeficiency virus [HIV]) and on-going infections and patients having clinical signs of on-going infections will be excluded from the study. Patients will be instructed to contact the principal investigator immediately if they have any sign of infection. In case of infection in a patient with low IgG plasma levels, intravenous immunoglobulin may be indicated.

It has been demonstrated in laboratory studies that IdeS cleaves biologics based on human IgG including; IVIg, basiliximab, rituximab, adalimumab, denosumab, belatacept and etanercept. IdeS also cleaves rabbit anti-thymocyte globulin (rATG) but not equine anti-thymocyte globulin (ATGAM). The optimal interval between HMedIdeS administration and these biologics have not been defined (HMed Doc. No. 2012-003). Rituximab is cleaved by IdeS and therefore rituximab treatment within 7 days prior to IdeS dosing will not be allowed in TTP patients. The concomitant use of these other biologics and IdeS will continue to be closely monitored in order to mitigate any changes in the efficacy of these biologics.

To date, there have been 3 reports of myalgia in completed studies, 1 was serious and unexpected and occurred in a patient with a previous history of myalgia to atorvastatin who was on chronic glucocorticoid treatment. The remaining 2 were non-serious. The non-serious cases resolved and the serious case was improving upon steroid tapering. Of note, an extensive workup including muscle biopsy, electromyograms and other muscle related biomarkers showed no abnormalities. Myalgias have been reported with treatment

with other biologics such as IVIg and rituximab (Orbach et al., 2005, Rituximab Summary of Product Characteristics).

Creatine kinase (CK) levels will be assessed in this study.

The patients will be closely monitored for all adverse events. The principal investigator must make sure that sufficient facilities and procedures are available to handle emergency situations during the study. The University College London Hospitals has extensive experience in early phase studies and there are adequate procedures in place to handle unexpected adverse reactions.

4. STUDY OBJECTIVES AND ENDPOINTS

4.1 Objectives

4.1.1 Primary Objective

To assess safety and tolerability of single intravenous doses of IdeS in patients diagnosed with asymptomatic antibody-mediated TTP with low ADAMTS13 activity

4.1.2 Secondary Objectives

To determine the following in patients diagnosed with asymptomatic antibody-mediated TTP with low ADAMTS13 activity

1. ADAMTS13 antigen, activity and antibody (IgG and F(ab')₂) levels following a single intravenous dose of IdeS during 64 days following IdeS dosing
2. Serum concentration of IdeS following a single intravenous dose of IdeS
3. Pharmacodynamic (PD) profile as measured by IgG levels and F(ab')₂ fragments concentrations during 64 days following IdeS dosing
4. Immunogenicity profile of IdeS

4.1.3 Exploratory Objectives

[REDACTED]

4.2 Endpoints

4.2.1 Primary Endpoint

Safety as measured by type, frequency and intensity of adverse events and change from baseline in parameters of clinical laboratory tests, vital signs and electrocardiograms (ECGs)

4.2.2 Secondary Endpoints

- Change from baseline in ADAMTS13 activity and antibody levels (IgG and F(ab')₂).
- Time for ADAMTS13 activity to return to normal levels
- Number of cases with normalisation of ADAMTS13 at 64 days
- Serum concentration of IdeS
- Change from baseline in pharmacodynamics as measured by level of IgG and F(ab')₂ fragments
- Immunogenicity of IdeS by measuring anti-drug antibodies

4.2.3 Exploratory Endpoints

- [REDACTED]

5. STUDY DESIGN

5.1 Overall Study Design

[figure not shown]

Figure 1. Overall schematic study design

This is a phase II, single arm study. The primary objective of the study is to assess safety and tolerability of IdeS in asymptomatic patients diagnosed with acquired TTP in clinical remission with ADAMTS13 activity less than 10% of normal levels. Secondary objectives include monitoring of ADAMTS13 activity and levels of ADAMTS13 antibodies. In addition, IdeS serum concentration, PD (total IgG and F(ab')₂ fragment concentrations) and immunogenicity profile of IdeS will be assessed.

Patients will be treated at the College University London Hospital, and will be subject to a single 30 minutes infusion with IdeS on day 0. Blood sampling for safety and efficacy will be performed and the patient will be closely monitored over a 24 h period after infusion after which they will be discharged. The follow-up visits will be in the out-clinic setting. Patients will receive premedication with paracetamol, Solu-Medrol and Loratidine before IdeS infusions. All patients will also receive a two-week regimen of prophylactic antibiotics starting pre-dose.

Following an evaluation of safety (clinical chemistry, haematology and coagulation and AEs) and efficacy in 3 patients receiving 0.25 mg/kg there will be a potential to increase the IdeS dose to 0.5 mg/kg for the remaining 3 patients.

5.2 Planned Number of Trial Sites and Subjects

The study will be conducted at one site, University College London Hospital, UK and will include 6 asymptomatic patients diagnosed with acquired TTP.

5.3 Decision Criteria for Dose Escalation

The decision for dose escalation to 0.5 mg/kg BW or an intermediary dose will be taken after the first 3 patients have been administered a dose of 0.25 mg/kg BW. The decision to escalate the dose will be a consensus between the Principal Investigator and the Sponsor. The safety, tolerability and efficacy of the dose will be evaluated prior to dose escalation. An internal monitoring committee (IMC) at Hansa Medical will review available safety and tolerability data after 3 patients have received a dose of 0.25 mg/kg before proceeding to the next dose. Safety data collected up to and including day 14 will be evaluated. The safety data will be compiled in an IMC package and also sent to the Principal Investigator for review. Safety data available for evaluation by the IMC and Principal Investigator before a dose escalation decision is shown in Table 3. In addition, ADAMTS13 activity,

ADAMTS13 antibodies and [REDACTED] will be included in the evaluation of a dose escalation. There will be at least 14 days between dosing of the first patient in a higher dose group and dosing of the last patient in the previous dose group.

If a Dose Limiting Toxicity (DLT) is demonstrated in one patient who has received a dose of 0.25 mg/kg BW and the underlying AE(s) is at least possibly related to the investigational drug, dose escalation will not occur and 3 additional patients will be administered 0.25 mg/kg. A well-tolerated 0.25 mg/kg dose may also be administered to the next three patients entered in the study if the pharmacodynamics effect of the dose is judged as satisfactory. A dose of 0.5 mg/kg BW or an intermediate dose may be given in the next three patients, if considered safe by the Principal Investigator and the Sponsor.

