5.5 Internal Monitoring Committee

An IMC will be formed and will be convened to assess safety data on each patient enrolled in the study. If at any time in the study, 2 or more patients have experienced a Grade 3 of related adverse event (NCI CTCAE v 4.0), the IMC will be convened. The IMC will also review a safety data package (Table 3) prior to dose escalation. An IMC charter will be written to pre-specify roles, responsibilities, procedures, and deliverables, as well as the purpose, scope, and timing of meetings.

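### The visible text of Protocol 5.3 and 5.5 does not hold dosing after a single dose-limiting toxicity, and no DLT rule covers doses above 0.25 mg/kg

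*Protocol*

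**What the plan says.** Protocol 5.4 defines a DLT as a novel adverse event of CTCAE grade 3 or more that is possibly related to the drug. One event in one patient is enough.

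Protocol 5.3 attaches a consequence to that event at one dose. The rule starts "If a Dose Limiting Toxicity (DLT) is demonstrated in one patient who has received a dose of 0.25 mg/kg BW" and, where the event is at least possibly drug-related, concludes that "dose escalation will not occur and 3 additional patients will be administered 0.25 mg/kg". For the higher level, 5.3 says only that 0.5 mg/kg or an intermediate dose "may be given in the next three patients, if considered safe by the Principal Investigator and the Sponsor".

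Protocol 5.5 gives the IMC three roles. One is general: "An IMC will be formed and will be convened to assess safety data on each patient enrolled in the study". One depends on events: "If at any time in the study, 2 or more patients have experienced a Grade 3 of related adverse event", the IMC is convened. The third is to review a safety package before escalation. Meeting times are deferred: "An IMC charter will be written to pre-specify roles, responsibilities, procedures, and deliverables, as well as the purpose, scope, and timing of meetings". The charter is not among the documents.

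**The concern.** A DLT definition protects patients when it is tied to an action taken before the next person is exposed. Here the only stated action concerns escalation. At 0.25 mg/kg a DLT blocks the higher dose but sends three more patients to the dose that produced it. Above 0.25 mg/kg a DLT has no stated consequence.

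The higher level is where prior experience is thinnest. For healthy volunteers, 3.6 states "Single doses up to 0.24 mg/kg BW (maximum dose tested) has previously been given to healthy volunteers". Patients with chronic kidney disease (CKD) reached 0.5 mg/kg only as two doses of 0.25 mg/kg. So in the completed studies that the protocol describes, 0.5 mg/kg was not given as one infusion. The patients in this trial are asymptomatic and in remission, and safety is the primary objective.

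**Working it through.** The plan has no figure to reproduce: 14.3 says that the sample size of six has no formal statistical basis, and no DLT rate is given. The check is whether any stated provision stops the next dose after one DLT.

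| Provision | What sets it off | Stated effect | Holds the next dose after one DLT? |
|---|---|---|---|
| 5.3, DLT rule | One DLT at 0.25 mg/kg | No escalation; 3 more patients at 0.25 mg/kg | No |
| 5.3, pre-escalation review | 3 patients dosed at 0.25 mg/kg, data to day 14 | Decision on the next dose level | Only the move to a new level |
| 5.3, dosing interval | Change of dose group | At least 14 days between groups | Not within a group |
| 5.3, higher-dose clause | Investigator and sponsor consider it safe | Three patients may receive it | No DLT condition given |
| 5.5, per-patient review | Each patient | IMC assesses the data | No time stated |
| 5.5, event trigger | Two or more patients with related Grade 3 events | IMC convened | No |
| 8.4.8, SAE reporting | A serious event | Report within 24 h | No; a DLT is defined by grade, not seriousness |
| 11.5, termination | Safety concerns | Sponsor may end the study | Discretionary; no DLT trigger |

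**What the stated rules permit.** These are maxima, counted with no assumed DLT rate, after a DLT in the first patient of a cohort.

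- At 0.25 mg/kg: 2 left in the cohort plus 3 additional patients, (3 − 1) + 3 = 5.
- At 0.5 mg/kg or an intermediate dose: 3 − 1 = 2.

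**How often the event trigger would stay silent.** Suppose all six patients are dosed, outcomes are independent, one DLT rate p applies at every dose, and a DLT and a related Grade 3 event are treated as the same thing. Then P(at least one DLT) = 1 − (1 − p)^6 and P(exactly one) = 6p(1 − p)^5. For p = 0.10, the second is 6 × 0.10 × 0.90^5 = 0.354.

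| Assumed p | P(at least one DLT in 6) | P(exactly one in 6) |
|---|---|---|
| 0.10 | 0.469 | 0.354 |
| 0.20 | 0.738 | 0.393 |
| 0.30 | 0.882 | 0.303 |
| 0.40 | 0.953 | 0.187 |
| 0.50 | 0.984 | 0.094 |

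The last column is the chance that a DLT occurs but the two-patient trigger is never met. These rates are assumptions, and the conclusion about the wording does not depend on them.

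**The case against.** The strongest reply is that oversight exists and that part of the plan is unseen. Protocol 5.5 has the IMC assess each patient without any two-patient threshold, so a single DLT at 0.5 mg/kg would reach it. Meeting timing is assigned to the charter, and a hold could be written there; the design figure is also not shown. This stands, and it limits the point to the visible text. It does not close the gap, because nothing visible says that the review must come before the next dose.

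It can also be said that 5.3 concerns escalation, so a rule for the top dose would not be expected there, and that its safety condition for the higher dose is not confined to one moment. Both are fair. They explain why 5.3 is silent, but neither supplies a DLT action elsewhere.

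Slow enrolment would help in practice. Taking the planned period as 275 to 455 days (the shortest and longest readings of Q2 2016 to Q2 2017), less 64 days of follow-up and 28 or 4 days of screening, even spacing over five gaps gives (275 − 64 − 28)/5 ≈ 37 to (455 − 64 − 4)/5 ≈ 77 days between patients. A review would often be possible in that time. The spacing is an average, however, and 5.3 sets no minimum within a dose group.

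The risk is tempered as well. Protocol 3.7 states that "the doses of 0.25 mg/kg and 0.5 mg/kg BW are well covered by the no observed adverse effect level (NOAEL) of 2.0 mg/kg BW" and reports an acceptable profile at a cumulative 0.5 mg/kg. Patients are observed for 24 h, and the sponsor may terminate the study.

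**Conclusion.** The point holds for the visible text. One DLT does not pause dosing, the 5.3 rule covers 0.25 mg/kg only, and the event trigger in 5.5 needs two patients and leads only to a meeting. It is a modest gap in a written rule, partly mitigated by the untimed per-patient review. Confidence is medium because the charter is not available.

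A reader might infer four stronger things that the documents do not support.

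- *That the higher-dose cohort had no safety review.* The per-patient review in 5.5 covers every patient.
- *That patients were harmed by the gap.* SAP section 1 reports that the sponsor stopped the study after two patients, following an IMC meeting, so the planned escalation never took place. That shows oversight acting, though it does not supply a pre-specified pause.
- *That a pause would spare 2 or 5 patients.* Those are ceilings on what the rules permit. A pause makes further dosing depend on a decision; the counts fall only if the IMC decides to stop.
- *That DLTs were likely.* The completed CKD study in 8 patients had four SAEs rated possibly or probably related. Their grades and the number of patients affected are not given, and such events may not count as novel under 5.4.

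**What to change.** State in 5.3 and 5.5, and repeat in the IMC charter:

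1. Any single DLT, as defined in 5.4, at any dose pauses further dosing until the IMC has reviewed it and decided whether dosing continues at that dose, continues at a lower dose or stops.
2. At 0.25 mg/kg the existing rule (no escalation, three additional patients) applies only if the IMC clears continued dosing.
3. The event trigger in 5.5 is lowered from two patients to one, to match.

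The cost is one extra IMC review and a short delay per DLT. If made after approval, a substantial change also needs regulatory and ethics approval before implementation (10.5). As this study has stopped, the practical use is in any later protocol that reuses this wording.

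I would not add a fixed day-7 wait between patients. The protocol's own window for the dose decision is day 14. Day 7 would miss later infections, and three of the four related SAEs in the CKD study were infections. In a cohort of three the wait could add up to 2 × 7 = 14 days, or 2 × 14 = 28 days with a day-14 cut-off. That is a trade-off for the trial team, whereas the pause after a DLT is not.
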